14.5 Sample Size and Power Calculations

SAFETY

The arms of five subjects are sized for safety, as the higher dose is expected to be necessary for an adequate immune response. In these arms (Arms 1a, 2a, 3a), 5 subjects each will receive 16 μg of Pfs25M-EPA/AS01 or 13 μg Pfs230D1M-EPA/AS01 or the combination of both.

Vaccination arms of 5 subjects gives a probability of at least 0.80 for detecting 1 or more serious or severe AEs that occur with a probability of 0.275 or more per subject.

For each dose level that has a ($n=10$) in Arms 1b, 2b, 3b, vaccination of 10 subjects gives a probability of at least 0.90 for detecting 1 or more serious or severe AEs that occur with a probability of 0.206 or more per subject.

For each dose level that has a (n=60) in Arms 2c, 2d, and 4c, vaccination of 60 subjects gives a probability of at least 0.90 for detecting 1 or more serious or severe AEs that occur with a probability of 0.038 or more per subject.

If we combine all treated groups in Mali (Arms 1a, 1b, 2a, 2b, 3a, 3b, 2c and 2d), 165 subjects, we have 95% power to detect 1 or more serious or severe AEs that occur with a probability of 0.018 or more per subject. Due to arms having varying doses, combinations and administration villages, this analysis would only be done to catch an AE that transcended these discrepancies.

We will compare all AE event proportions between the control arm and treated arm by Fisher's exact test.

ELISA ANALYSIS

There are several questions of interest based on the antibody response information after the 2nd, 3rd and for arms 2c, 2d, and 4c, a 4th (booster) doses of the respective vaccines. We are interested in the change in ELISA values from baseline to after a given number of doses of vaccine, and the change in ELISA values between doses. For this we will use Wilcoxon signed rank tests (WSRT) within the 60 subjects receiving a given vaccine regimen. We are also interested in the effect of a given number of vaccinations on the ELISA responses as compared to comparator. This comparison can be made by Wilcoxon Mann Whitney (WMW) test, which accommodates the limit of detection issues that may exist for ELISA results.

The preliminary data from protocol #15-I-0044 on subjects who had each Pfs25 and Pfs230 ELISA measurements after receiving two and three doses of 47µg Pfs25 + 40µg Pfs230 (using Alhydrogel[®] adjuvant, not AS01 as in this protocol) allow us to estimate the SD of the log transformed Pfs25 ELISA responses at baseline, post vaccination 2 and post vaccination 3. Due to these data still being blinded, we do not report the values for the SD and mean of the log transformed Pfs25 ELISA responses.

Assuming similar values in this trial, there would be over 0.99 power to detect the difference between baseline and post-vaccination 2 and over 0.9 power to detect the difference between post vaccination 2 and post vaccination 3.

In these same preliminary data from protocol #15-I-0044 all control subjects had undetectable levels of Pfs25 ELISA response post 2nd and 3rd vaccination.

Within Arm 2c and using the background information from #15-I-0044, we have greater than 80% power to reject a 2-sided 0.05 level WMW test if the geometric mean Pfs230 ELISA baseline level was 1.6-fold higher geometric mean than the level of detection in the vaccinated group post vaccination 2 (Note: 1.6-fold is lower than what we observed in #15-I-0044, so we treat these numbers as conservative). Given the similarity in SD estimate post vaccination 3, we should have very similar power post vaccination 3 as was calculated for post vaccination 2.

There are three key comparisons regarding ELISA measurements and the booster dose (equivalently dose 4). These include 1) peak titers after dose 4 compared with those following

dose 3; 2) nadir titers at 3 months post dose 4 compared to those post dose 3; and 3) decay rates after dose 4 compared to those after dose 2 and those after dose 3. The power to detect these differences is modest/low due to the expected performance of the booster to perform similarly to the previous doses. However, it is important to note that the primary immunogenicity endpoints will be comparing ELISA titers of each arm 2c and 2d versus the control arm 4c at all time points, which will be powered above 90%.

FUNCTIONAL ASSAYS

SMFA

Using blinded SMFA data from #15-I-0044, a WMWT comparing 60 TRAs of the vaccine arm to 60 TRAs of the control, we anticipate at least 80% power to detect a difference in TRAs of 18% (simulation-based power calculations). If TBAs are used, we will standardize the TBAs to a common target control mean first. The standardization will utilize the estimand that comes from a zero-inflated negative binomial with random effects for feed and container of mosquito. TRAs can be combined across feeds or calculated within feeds as they do not require the same standardization as that of TBAs.

DSF

Using the data from the primary DSF evaluation period of study #13-I-N109 and #15-I-0044 we were able to do power calculations for this study. The power calculations are quite sensitive to the infectivity rate, which varies from year to year. Taking a weighted average of 2014 and 2015 data we estimate infectivity was 14.8% (the percentage of subjects in the control arm that had at least one positive DSF). Using this same % and comparing 108 subjects (this number assumes 10% dropout) of the combined Arms 2c and 2d we will have ~85% power to detect 80% vaccine effect through the (0,1) infective/non-infective way of quantifying each DSF with 32 DSF per person and 30 mosquitoes per cup. The (0,1) infective/non-infective way of quantifying each DSF involves declaring a cup as infective if any of the 30 mosquitoes is infected and conversely non-infective if and only if all 30 mosquitoes are not infected. While combining arms that have full dosing in one and fractional dosing in the other assumes they are having similar effects, this assumption is deemed acceptable in order to power the analysis. If infectivity drops to 10.3%, then the power to detect 80% vaccine effect under same conditions is about 40%. It is important to note that in 2016 only 15 mosquitoes were used per cup and only 12 DSFs per person were conducted. Thus, we are treating the 10.3% infectivity as a “worse case scenario” for the 30 cup / 24 DSFs set-up as proposed in this protocol. A binomial family GEE model will be used to account for repeated measurements.

On average each feed week we had about 3% positivity over all subjects. The (0,1) infective/non-infective way of quantifying DSF is likely an over-simplification of the true system. As well, this way of quantifying the DSF will have lower power when the vaccine is leaky rather than all or nothing.

For the booster (dose 4), the combined Arms 2c and 2d will be evaluated vs. controls as the primary endpoint.

DSF in conjunction with SMFA

As there will be simultaneous blood draws, a unique opportunity to investigate SMFA predicting zero inflated DSF measurements will be pursued. Simple linear regression models will be explored.

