A summary of immune responses and functionality results are provided below in **Figure 20** and **Figure 21**. In brief, while there was a significant difference between the full and fractional arms detected by antibody responses to Pfs230 (as seen in **Figure 20** with $p=0.00014$), functional activity by SMFA showed no significant difference between the two groups ($p=0.0597$, **Figure 21**). The similarity in SMFA responses may be due to antibody titers remaining elevated above a possible threshold that may provide high levels of TRA at 12 weeks post-vaccination. These levels would be expected to decrease over time allowing for analysis of the difference of the effectiveness of the two doses at later timepoints. With no clearly superior regimen evident after a third vaccination with either a full or a fractional dose of Pfs230, we will plan to assess a full boosting dose in both Arms 2c and 2d. This approach was also recommended in recent discussion with the DSMB.

Figure 20 : Antibody responses to Pfs230 at 12 weeks post-vaccination #3 with either full or fractional dosing

[figure not shown]

Figure 20: Antibody responses to Pfs230 at 12 weeks post-vaccination #3 with either full or fractional dosing.

Participants in the fractional dosing group (Arm 2d) received 8 μ g Pfs230 for their third vaccination, while full dosing (Arm 2c) group received 40 μ g Pfs230 for their third vaccination. Both groups received 40 μ g Pfs230 for their first and second vaccinations. Wilcoxon p values for comparisons between arms are as follows: Full vs. Fractional: $p=0.00014$; Full vs. Control: $p<0.0001$; Fractional vs. Control: $p<0.0001$.

Figure 21: Functional activity of Pfs230 by SMFA at 12 weeks post-vaccination #3 with either full or fractional dosing

[figure not shown]

Figure 21: Functional activity of Pfs230 by SMFA at 12 weeks post-vaccination #3 with either full or fractional dosing. Participants in the fractional dosing group (Arm 2d) received 8 μ g Pfs230 for their third vaccination, while full dosing group (Arm 2d) received 40 μ g Pfs230 for their third vaccination. Both groups received 40 μ g Pfs230 for their first and second vaccinations. Wilcoxon p values for comparisons between arms are as follows: Full vs. Fractional: $p=0.0597$; Full vs. Control: $p<0.0001$; Fractional vs. Control: $p<0.0001$.

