5.1 Overall Design

This is a phase 1 study designed to evaluate safety, reactogenicity, immunogenicity, and transmission-blocking activity (via SMFA) of Pfs25M-EPA and Pfs230D1M-EPA conjugates formulated on AS01 and transmission-blocking activity (via DSF) of Pfs230D1M-EPA conjugates formulated on AS01 at full and fractional dosing. We will enroll a total of 305 vaccinated subjects to be divided between multiple sites in Mali as shown in [Appendix A](#) and described below.

In Bamako/Sotuba, Mali (N=65)

Dose-escalating, open label, randomized, pilot study

1. Group 1: Pfs25M-EPA/AS01 (n=15)

- **Arm 1a** (n=5), to receive 16 µg Pfs25M-EPA/AS01 on D0, D28, D168
- **Arm 1b** (n=10), to receive 47 µg Pfs25M-EPA/AS01 on D0, D28, D168

2. Group 2: Pfs230D1M-EPA/AS01 (n=15)

- **Arm 2a** (n=5), to receive 13 µg Pfs230D1M-EPA/AS01 on D0, D28, D168
- **Arm 2b** (n=10), to receive 40 µg Pfs230D1M-EPA/AS01 on D0, D28, D168

3. Group 3: Pfs25M-EPA/AS01 and Pfs230D1M-EPA/AS01 (n=15)

- **Arm 3a** (n=5), to receive 16 µg Pfs25M-EPA/AS01 and 13 µg Pfs230D1M-EPA/AS01 on D0, D28, D168
- **Arm 3b** (n=10), to receive 47 µg Pfs25M-EPA/AS01 and 40 µg Pfs230D1M-EPA/AS01 on D0, D28, D168

4. Group 4: Comparator (n=20)

- **Arm 4a** (n=10), to receive ENGERIX-B on D0, D28, and D168
- **Arm 4b** (n=10), to receive ENGERIX-B on D0, D28, and D168

In Bancoumana and Doneguebougou, Mali (N=240)

Double-blind, randomized, phase 1 clinical trial

1. Group 2: Pfs230D1M-EPA/AS01 (n=120)

- **Arm 2c** (n=60), to receive 40 µg Pfs230D1M-EPA/AS01 on D0, D28, D168, and a fourth dose of 40 µg on D476
- **Arm 2d** (n=60), to receive 40 µg Pfs230D1M-EPA/AS01 on D0, D28, then 8 µg Pfs230D1M-EPA/AS01 (*fractional dose*) on D168, and a fourth dose of 40 µg on D476

2. Group 4: Comparators (n=120)

- **Arm 4c** (n=120), to receive ENGERIX-B on D0, D28, and D168 (start study with Arm 2c and 2d), and Menactra[®] on D476.

The multisite study in Mali is designed in a stepwise manner such that each dose of the TBVs is administered in a dose-escalating fashion, and each vaccine (either Pfs25M-EPA/AS01 or Pfs230D1M-EPA/AS01) is administered first as a single vaccination at the target dose before it is administered simultaneously. Additionally, two doses of each vaccine will be administered and assessed for safety as outlined in **Section 12.14.4** and **Appendix A** prior to implementation of the first vaccination in the double blind portion of the study.

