14.6 Randomization

See [Section 8.2](#) for more information.

Enrollment into the Bamako/Sotuba, Mali portion of the study will be randomized as follows:

- Arms 1a and 2a will be enrolled 1-1 with random block based on time of enrollment/randomization;
- Arm 3a will not have a concurrent arm, so there will be no randomization for that arm;
- Arms 1b, 2b and 4a will be enrolled 1-1-1 with the same style of random block based on time of enrollment/ randomization;
- Arms 3b and 4b will be enrolled 1-1 with random block based on time of enrollment/randomization.

Enrollment into the Bancoumana/Doneguebougou, Mali portion of the study will be randomized in random blocks of size no greater than 8 and stratified by village. In order to accomplish this, a list of all enrolled subjects will be given to the study statistician for the first randomization. As subjects that dropout after randomization, and are not vaccinated, cannot be replaced, randomization and first vaccination should occur as close in time as possible to avoid having subjects in the ITT efficacy and safety analyses that have never received vaccination or comparator. Randomization lists are not produced pre-enrollment to reduce the risk of on-site operational error in randomization assignment, which given the stratified nature of the randomization would require management of several lists.

Randomization will occur **between arms** as follows in the Bancoumana/Doneguebougou study:

- Arms 2c, 2d, and 4c will be enrolled 1-1-2 with random block sizes no greater than 8.

Randomization between the arms allows for causal comparisons of ELISA and functional assay responses.

15 Human Subject Protections and Ethical Obligations

This research will be conducted in compliance with the protocol, Good Clinical Practices (GCP), and all applicable regulatory requirements.

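### Arms 2c and 2d are one randomised treatment until Day 168, but Section 14.5 sizes safety on 60, lists Arm 4c (120 subjects) under n=60, and names no combined 2c+2d analysis for doses 1 and 2

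*Combined protocol and SAP*

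**What the plan says.** Section 5.1 (Overall Design) gives Arm 2c, at the 40 µg dose, "Pfs230D1M-EPA/AS01 on D0, D28, D168, and a fourth dose of" 40 µg. Arm 2d receives the same 40 µg dose, "Pfs230D1M-EPA/AS01 on D0, D28, then" the fractional dose on Day 168. Section 3.5.2.2 confirms that both groups had 40 µg "Pfs230 for their first and second vaccinations". The comparator, Arm 4c, is "n=120), to receive ENGERIX-B on D0, D28, and D168 (start study with Arm 2c and 2d". Section 14.6 randomises the three together: "Arms 2c, 2d, and 4c will be enrolled 1-1-2 with random block sizes no greater than 8", stratified by village.

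Section 14.5 begins its safety sizing for the main study with the words "For each dose level that has a (n=60) in Arms 2c, 2d, and 4c, vaccination of 60 subjects". Its claim for a group of that size is that it "gives a probability of at least 0.90 for detecting 1 or more serious or severe AEs that occur with a probability of 0.038". For antibody data it plans signed-rank tests within the 60 subjects on a given regimen. It then says that the primary immunogenicity endpoints "will be comparing ELISA titers of each arm 2c and 2d versus the control arm 4c at all time points", with power above 90%.

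Arms 2c and 2d are combined in three places in Section 14.5: the DSF power calculation, the booster comparison, and a 165-subject safety pool of all vaccinees. That pool mixes antigens and doses and is reserved for an event common to all arms.

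The safety comparison itself is loosely worded. Section 14.2 allows grouping by schedule and/or dose, and Section 14.5 contrasts a control arm with a treated arm without saying which arms form the treated side.

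**The concern.** Until the third vaccination, the labels 2c and 2d carry no treatment difference. Combining randomised arms that are still identical needs no assumption about effect. Combining them after dose 3 does need one, as Section 14.5 admits for DSF. The plan therefore combines the arms where an assumption is required and names no 2c+2d combination where none is.

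Two things are at stake. The first is precision for the primary endpoint. Section 14.1 says that the study exists to estimate adverse event rates and immune response patterns, and the stated sizing for the first two 40 µg doses uses half of the main-study subjects who receive them. The second is interpretation. If each arm is tested against the same controls on data from before Day 168, one treatment is tested twice. One result can reach significance and the other not, which a reader could take for a regimen difference that cannot yet exist.

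Separately, counting Arm 4c as 60 is a plain error in the stated figure.

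**Working it through.** **Inputs from the documents.** Arms 2c, 2d and 4c have 60, 60 and 120 subjects (Section 5.1). The arms first differ on Day 168. The detection statement is 0.90 at a rate of 0.038 with n=60. The ELISA test is two-sided at 0.05, with greater than 80% power for a 1.6-fold difference in Arm 2c (Section 14.5).

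**1. The plan's own safety figure.** The probability of at least one event is 1 − (1 − p)^n.
- n=60, p=0.038: 1 − 0.962^60 = 0.902, as stated.
- The rate giving exactly 0.90 is 1 − 0.1^(1/60) = 0.0376.
- The other stated figures also reproduce: n=5 at 0.275 gives 0.800; n=10 at 0.206 gives 0.900; n=165 at 0.018 gives 0.950.

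**2. The same figure with 120 subjects** (2c+2d at doses 1 and 2, or Arm 4c).
- Rate for 0.90: 1 − 0.1^(1/120) = 0.0190.
- Chance of at least one event at a true rate of 0.019: 0.684 with 60, 0.900 with 120.
- At a true rate of 0.038: 0.902 with 60, 0.990 with 120.
- With the 10% dropout that Section 14.5 uses for DSF (54 and 108 subjects), the rates are 0.042 and 0.021, so the halving is unaffected.

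**3. Precision.**
- Standard error of the vaccine-group mean: √(60/120) = 0.707, a fall of 29%.
- Standard error of the difference from 4c: √(1/120 + 1/120) / √(1/60 + 1/120) = 0.816, a fall of 18%.

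**4. Comparing adverse event proportions (illustration only).** The event rates below are assumptions, since the documents give none for this purpose. The calculation is exact for a two-sided Fisher test at 0.05. The last column is the chance that exactly one of the two separate tests (2c v 4c, 2d v 4c) is significant.

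| Control v vaccine | Power, 60 v 120 | Power, 120 v 120 | Separate tests disagree |
|---|---|---|---|
| 5% v 15% | 0.56 | 0.67 | 0.38 |
| 10% v 25% | 0.70 | 0.84 | 0.34 |
| 30% v 45% | 0.47 | 0.63 | 0.39 |
| 30% v 50% | 0.71 | 0.87 | 0.33 |

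With no effect (30% v 30%), the chance that at least one of the two separate tests is significant is 0.08, against 0.04 for the single combined test.

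**5. ELISA.** The plan withholds the standard deviation, so its power cannot be reproduced. It can be rescaled by normal approximation. With V = 1/n₁ + 1/n₀, power = Φ[(1.96 + 0.84)·√(V_base/V_new) − 1.96]. The plan does not say which control size its 80% refers to, so both readings are shown.
- If the 80% is for 60 v 60: 60 v 120 gives Φ(2.80 × √(0.0333/0.0250) − 1.96) = 0.90, and 120 v 120 gives 0.98.
- If it is for 60 v 120: 120 v 120 gives Φ(2.80 × √1.5 − 1.96) = 0.93, and the fold difference detectable at 80% power falls from 1.60 to 1.47.

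**6. SMFA.** Appendix C lists no SMFA sample for Arms 2c, 2d and 4c before Day 168; the first is Day 182. There is nothing to combine.

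**The case against.** A reader might infer that half of the vaccinees are discarded. They are not: both arms are analysed and reported.

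A reader might also infer that adverse events must be tested arm by arm throughout. The documents do not say so. Testing each arm at all time points is written only for ELISA. The safety wording in Sections 14.2 and 14.5 would permit grouping by dose, and before Day 168 Arms 2c and 2d are one dose group. The sentence about 60 subjects is a detection statement, not an analysis rule, and 60 is the correct size for each arm's third dose. This stands, but it leaves the comparison group for the primary endpoint undefined and the only sizing for this dose level at 60.

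The 165-subject pool does include both arms, so it would be wrong to say that they are combined only for DSF and the booster. Its restricted use and mix of products mean that it does not replace a 2c+2d analysis.

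The antibody gain is small. Section 14.5 already claims over 0.99 power for baseline to post-vaccination 2 and above 90% against control, and calls the 1.6-fold figure conservative. Discordant ELISA results are therefore unlikely; both arms had p<0.0001 against control 12 weeks after dose 3 (Section 3.5.2.2).

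Finally, the study describes itself as exploratory, and the scheduled unblinding has taken place. The sizing text can no longer change the trial, and a new combined analysis would be a late addition. That is a fair limit. However, the reason for combining lies in the design and not in the results.

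**Conclusion.** The point holds in a limited form. Before the Day 168 dose, Arms 2c and 2d are one randomised treatment of 120 against 120 controls, and the plan names no analysis that treats them so. The consequence is a loss of precision, mainly for adverse events: the rate detectable with probability 0.90 is 0.019 rather than 0.038, and the standard error against control would be 18% smaller. Where the arms are tested separately, one treatment is also tested twice. For antibody data the practical gain is minor. Listing Arm 4c under n=60 is an error whatever is decided about combining.

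The detection figures rest only on the arm sizes and on independent subjects with a common event rate. The Fisher powers and disagreement rates depend on assumed event rates and are illustrations. The ELISA rescaling depends on a normal approximation and on which control size the stated 80% refers to.

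**What to change.** In Sections 14.2, 14.3 and 14.5, state that safety and ELISA data collected before the Day 168 dose are analysed as combined Arms 2c+2d (n=120) against Arm 4c (n=120), with signed-rank tests within the combined 120, and that these outcomes are analysed by separate arm from Day 168 on. Label the combined analysis as added after the scheduled unblinding. No SMFA change is needed.

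Correct Arm 4c to n=120 in the safety sizing. Restate the 0.90 detection probability as an event rate of 0.019 for the 40 µg dose at doses 1 and 2 and for Arm 4c, and keep 0.038 for each arm's third dose.

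The cost is a few sentences and one extra column in the tables. The one small downside is that the analysis must be reported as specified after unblinding.
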